6.6 Criteria for removal from study

Patients will be removed from study when any of the criteria listed below applies. The reason for study removal and the date the patient was removed must be documented in the Case Report Form.

In the absence of treatment delays due to adverse event(s), treatment may continue until one of the following criteria applies:

- Disease progression,
- Intercurrent illness that prevents further administration of treatment,
- Unacceptable adverse event(s),
- Patient decides to withdraw from the study, or
- General or specific changes in the patient's condition render the patient unacceptable for further treatment in the judgment of the treating and/or lead investigator.
- Patient refusal
- Patient withdrawal
- Administrative reasons after discussion/approval by the Lead Investigator
- Lost to follow-up/Non-compliance
- Study termination

6.7 Study drug(s)

6.7.1 Packaging and labeling

BGJ398 (infigratinib) will be supplied by Novartis as 25mg and 100mg-mg hard gelatin capsules for oral use, packaged in bottles, and will be administered on a flat scale.

Medication will be labeled for Clinical Trial use and will include storage conditions for the drug and the medication number but no information about the patient.

Table Packaging and labeling

Study drugs	Packaging	Labeling
BGJ398 (infigratinib)	hard gelatin capsules in bottles (25mg, 100mg)	Labeled as "BGJ398 (infigratinib)"

6.7.2 Supply, receipt and storage

Study drug must be received by a designated person at the study site, handled and stored safely and properly, and kept in a secured location to which only the site investigator and designated study staff have access. Upon receipt, BGJ398 (infigratinib) should be stored according to the instructions specified on the drug labels. Study medication will be dispensed by an authorized person at the investigator's site.

Patients will be provided with adequate supply of BGJ398 (infigratinib) for self-administration at home until at least their next scheduled study visit.

6.7.3 Drug compliance and accountability

Patients will be required to keep a pill diary (see Section 11.3 Appendix C for sample medication diary). Pill count will be performed at the end of each cycle to confirm drug compliance.

Clinical drug supply must be accounted for and patients will be asked to return all unused study drug and packaging on a regular basis, at the end of the study or at the time of study drug discontinuation.

At the conclusion of the study, and, as appropriate during the course of the study, the Site Investigator will return all used and unused study drug, packaging, drug labels, and a copy of the completed drug accountability ledger to Novartis.

6.7.4 Disposal and destruction

The drug supply will either be destroyed at a Novartis facility or the investigational study site. Novartis will provide guidelines for destruction, if investigational site is approved to destroy drug per prior agreement with Novartis.

6.7.5 Study drug discontinuation

Patients who discontinue study treatment should be scheduled for an End of Study Visit within 14 days after discontinuing study treatment, at which time all of the assessments listed for the End of study visit will be performed. Patients lost to follow up should be recorded as such.

All patients who discontinue study treatment (or a knowledgeable informant), including those who refuse to return for the final 14-day Follow up Visit, should be contacted for safety evaluations, anti-neoplastic therapies received after discontinuation of study drug, and overall survival \leq 30 days following the last dose of study treatment.

Patients whose treatment is interrupted or permanently discontinued due to a study-related adverse event or abnormal laboratory value must be followed 30 days post study discontinuation until all toxicities have resolved to CTCAE \leq 1 or until stabilization.

Patients whose treatment is interrupted or permanently discontinued due to any dose-limiting ocular/visual toxicity will have appropriate follow-up ophthalmologic examinations weekly until the toxicity has completely resolved or until the toxicity is considered to have stabilized after at least 6 months of follow-up. Refer to section on Clinical Safety.

	Screening	Treatment									Subsequent cycles	End of treatment / End of study visit	End of Post-treatment follow-up	Survival
		Cycle 1				Cycle 2				Cycle 3+ Visits on day 1 of each cycle unless more frequent visits are clinically indicated				
Visit no.	1 ¹	2	3	4	5	6	7	8	9	10+				
Day of cycle	Screening / Baseline	1	8	15	21	1	8	15	21	1		EOT*	End of Post-treatment follow-up	Survival**
Radiological tumor assessment/ response assessment (CT Scans) ⁴	X										Every uneven treatment cycle and +/- 8 days of D1 of respective cycle	X		
Hematology ⁵	X	X	X	X	X	X		X		X		X		
Serum Chemistry ⁶	X	X	X	X	X	X		X		X		X		
Pregnancy Test ⁷	X (blood)	X				X				X		X		
LVEF assessment ¹⁰	X	To be repeated every 4-6 months in asymptomatic patients. In symptomatic patients, LVEF assessment should be done every 2-4 months and more frequently as needed if symptoms occur/clinically indicated												
BGJ398 (infigratinib) dosing ⁸		Continuous (21 days with 7 days of rest)												
Tumor biopsy ⁹		In responders with progressive disease												
Prophylactic phosphate-lowering therapy		Daily												
Concomitant medications		Continuous monitoring												

⁷ All women of child bearing potential (pre-menopausal or less than 1 year after the onset of menopause, and intact uterus) must have a serum pregnancy test (β -hCG) ≤ 72 hours before the first dose of study treatment. Additionally, a urine pregnancy test should be performed at Day 1 of each cycle and at the End of Treatment visit (serum test is acceptable as an alternative). A positive pregnancy test requires immediate interruption of study drug treatment until serum β -hCG is performed and found to be negative. If positive, the patient must be discontinued

Pregnancy testing is only required in woman with child bearing potential (pre-menopausal women with intact uterus)

⁸ BGJ398 (infigratinib) is taken daily (21 days on with 7 days of rest) and self-administered by the patient. Medication cannot be administered through G tube. Treatment courses continue until disease progression or unacceptable drug intolerance. Patient is supplied a new bottle of study drug on days 1 of each cycle (each bottle contains 30 tablets).

⁹ Patients who demonstrate initial clinical and/or radiographic response (e.g. tumor shrinkage) to therapy, followed by subsequent progressive disease by RECIST, should proceed with mandatory tissue biopsy for biomarker correlative studies in event of accessible tumor tissue.

¹⁰ LVEF assessment can be done by MUGA scan or Echocardiogram. A prior normal LVEF assessment in the past 6 months in the absence of cardiac symptoms is acceptable as a baseline assessment.

* A scan performed for clinical reasons mid-cycle (e.g., for clinical symptoms of possible disease progression) which confirms progressive disease and which results in the patient being taken off study, will count as the end of treatment radiologic evaluation.

** Patients will be followed for survival status, and time of death, though this is not a primary endpoint of the study. See section 4.5 and 10.6.

* Tests should be performed within ± 8 days of the scheduled day of assessment during treatment period with BGJ398 (infigratinib).

****Ophthalmic exam should** include: visual acuity testing, slit lamp examination of the anterior eye segment, IOP, and funduscopy. Additional examination methods such as specular microscopy (that enables a magnified, direct view of the corneal epithelium), corneal pachymetry, and dilated funduscopy. Ophthalmic exams should be done at baseline and after two cycles (=beginning of cycle 3). In addition ophthalmic exams should be done as clinically indicated.

7.2 Screening Examination

Baseline evaluations are to be conducted within 14 days prior to start of protocol therapy. Scans and x-rays must be done < 28 days prior to the start of therapy. In the event that the patient's condition is deteriorating, laboratory evaluations should be repeated within 48 hours prior to initiation of the next cycle of therapy. The screening examination must start with the Informed Consent procedure. The treating investigator is obliged to give the patient thorough information about the study and the study related assessments, and the patient should be given ample time to consider his or her participation. The treating investigator must not start any study related procedure before ICF is signed and dated by both patient (and impartial witness, if applicable) and investigator.

7.3 Assessment types

7.3.1 Efficacy

Efficacy will be assessed through RECIST 1.1 defined objective response rate (e.g. ORR, complete or partial response).

Per RECIST 1.1, investigators are to obtain confirmatory scans greater than 4 weeks after objective response ([Eisenhauer EA et al, Eur J Ca, 2009](#)).

For the purposes of this study, patients should be reevaluated for response every 8 weeks. Response and progression will be evaluated in this study using the new international criteria proposed by the revised Response Evaluation Criteria in Solid Tumors (RECIST) guideline (version 1.1) ([Eisenhauer EA et al, Eur J Ca, 2009](#)). Changes in the largest diameter (unidimensional measurement) of the tumor lesions and the shortest diameter in the case of malignant lymph nodes are used in the RECIST criteria.

Definitions

Evaluable for toxicity. All patients will be evaluable for toxicity from the time of their first treatment with BGJ398 (infigratinib).

Evaluable for objective response. Only those patients who have measurable disease present at baseline, have received any therapy with BGJ398 (infigratinib), and have had their disease re-evaluated (= at least one post-baseline scan is available) will be considered evaluable for response. These patients will have their response classified according to the definitions stated below. (Note: Patients who exhibit objective disease progression prior to the end of cycle 2 (i.e. clinically indicated scan ahead of schedule shows progressive disease) will also be considered evaluable.)

Evaluable Non-Target Disease Response. Patients who have lesions present at baseline that are evaluable but do not meet the definitions of measurable disease, have received any therapy with BGJ398 (infigratinib), and have had their disease re-evaluated will be considered evaluable for non-target disease. The response assessment is based on the presence, absence, or unequivocal progression of the lesions.

Disease Parameters

Measurable disease is defined per RECIST 1.1 ([Eisenhauer et al Eur J Cancer 2009](#))

Note: Tumor lesions that are situated in a previously irradiated area might or might not be considered measurable. *If the investigator thinks it appropriate to include them, the conditions under which such lesions should be considered must be defined in the protocol.*

Malignant lymph nodes are defined per RECIST 1.1 ([Eisenhauer et al Eur J Cancer 2009](#))

Non-measurable disease is defined per RECIST 1.1 (Eisenhauer et al Eur J Cancer 2009)

Target lesions nodes are defined per RECIST 1.1 (Eisenhauer et al Eur J Cancer 2009)

Non-target lesions nodes are defined per RECIST 1.1 (Eisenhauer et al Eur J Cancer 2009)

Methods for Evaluation of Measurable Disease

Analogous to outlined methods in RECIST 1.1 nodes are defined per RECIST 1.1 (Eisenhauer et al Eur J Cancer 2009). Briefly:

All measurements should be taken and recorded in metric notation using a ruler or calipers. All baseline evaluations should be performed as closely as possible to the beginning of treatment and never more than 4 weeks before the beginning of the treatment.

The same method of assessment and the same technique should be used to characterize each identified and reported lesion at baseline and during follow-up. Imaging-based evaluation is preferred to evaluation by clinical examination unless the lesion(s) being followed cannot be imaged but are assessable by clinical exam.

Clinical lesions. Clinical lesions will only be considered measurable when they are superficial (*e.g.*, skin nodules and palpable lymph nodes) and ≥ 10 mm diameter as assessed using calipers (*e.g.*, skin nodules). In the case of skin lesions, documentation by color photography, including a ruler to estimate the size of the lesion, is recommended.

Chest x-ray. Lesions on chest x-ray are acceptable as measurable lesions when they are clearly defined and surrounded by aerated lung. However, CT is preferable.

Conventional CT and MRI. This guideline has defined measurability of lesions on CT scan based on the assumption that CT slice thickness is 5 mm or less. If CT scans have slice thickness greater than 5 mm, the minimum size for a measurable lesion should be twice the slice thickness. MRI is also acceptable in certain situations (*e.g.* for body scans).

Use of MRI remains a complex issue. MRI has excellent contrast, spatial, and temporal resolution; however, there are many image acquisition variables involved in MRI, which greatly impact image quality, lesion conspicuity, and measurement. Furthermore, the availability of MRI is variable globally. As with CT, if an MRI is performed, the technical specifications of the scanning sequences used should be optimized for the evaluation of the type and site of disease. Furthermore, as with CT, the modality used at follow-up should be the same as was used at baseline and the lesions should be measured/assessed on the same pulse sequence. It is beyond the scope of the RECIST guidelines to prescribe specific MRI pulse sequence parameters for all scanners, body parts, and diseases. Ideally, the same type of scanner should be used and the image acquisition protocol should be followed as closely as possible to prior scans. Body scans should be performed with breath-hold scanning techniques, if possible.

PET-CT. At present, the low dose or attenuation correction CT portion of a combined PET-CT is not always of optimal diagnostic CT quality for use with RECIST measurements. However, if the site can document that the CT performed as part of a PET-CT is of identical diagnostic quality to a diagnostic CT (with IV and oral contrast), then the CT portion of the PET-CT can be used for RECIST measurements and can be used interchangeably with conventional CT in accurately measuring cancer lesions over time. Note, however, that the PET portion of the CT introduces additional data which may bias an investigator if it is not routinely or serially performed.

Ultrasound. Ultrasound is not useful in assessment of lesion size and should not be used as a method of measurement. Ultrasound examinations cannot be reproduced in their entirety for independent review at a later date and, because they are operator dependent, it cannot be guaranteed that the same technique and measurements will be taken from one assessment to the next. If new lesions are identified by ultrasound in the course of the study, confirmation by CT or MRI is advised. If there is concern about radiation exposure at CT, MRI may be used instead of CT in selected instances.

Endoscopy, Laparoscopy. The utilization of these techniques for objective tumor evaluation is not advised. However, such techniques may be useful to confirm complete pathological response when biopsies are obtained or to determine relapse in trials where recurrence following complete response (CR) or surgical resection is an endpoint.

Tumor markers. Tumor markers alone cannot be used to assess response. If markers are initially above the upper normal limit, they must normalize for a patient to be considered in complete clinical response. Specific guidelines for both CA-125 response (in recurrent ovarian cancer) and PSA response (in recurrent prostate cancer) have been published [*JNCI* 96:487-488, 2004; *J Clin Oncol* 17, 3461-3467, 1999; *J Clin Oncol* 26:1148-1159, 2008]. In addition, the Gynecologic Cancer Intergroup has developed CA-125 progression criteria which are to be integrated with objective tumor assessment for use in first-line trials in ovarian cancer [*JNCI* 92:1534-1535, 2000].

Cytology, Histology. These techniques can be used to differentiate between partial responses (PR) and complete responses (CR) in rare cases (*e.g.*, residual lesions in tumor types, such as germ cell tumors, where known residual benign tumors can remain).

The cytological confirmation of the neoplastic origin of any effusion that appears or worsens during treatment when the measurable tumor has met criteria for response or stable disease is mandatory to differentiate between response or stable disease (an effusion may be a side effect of the treatment) and progressive disease.

FDG-PET While FDG-PET response assessments need additional study, it is sometimes reasonable to incorporate the use of FDG-PET scanning to complement CT scanning in assessment of progression (particularly possible 'new' disease). New lesions on the basis of FDG-PET imaging can be identified according to the following algorithm:

- a. Negative FDG-PET at baseline, with a positive FDG-PET at follow-up is a sign of PD based on a new lesion.
- b. No FDG-PET at baseline and a positive FDG-PET at follow-up: If the positive FDG-PET at follow-up corresponds to a new site of disease confirmed by CT, this is PD. If the positive FDG-PET at follow-up is not confirmed as a new site of disease on CT, additional follow-up CT scans are needed to determine if there is truly progression occurring at that site (if so, the date of PD will be the date of the initial abnormal FDG-PET scan). If the positive FDG-PET at follow-up corresponds to a pre-existing site of disease on CT that is not progressing on the basis of the anatomic images, this is not PD.
- c. FDG-PET may be used to upgrade a response to a CR in a manner similar to a biopsy in cases where a residual radiographic abnormality is thought to represent fibrosis or scarring. The use of FDG-PET in this circumstance should be prospectively described in the protocol and supported by disease-specific medical literature for the indication. However, it must be acknowledged that both approaches may lead to false positive CR due to limitations of FDG-PET and biopsy resolution/sensitivity.

Note: A 'positive' FDG-PET scan lesion means one which is FDG avid with an uptake greater than twice that of the surrounding tissue on the attenuation corrected image.

Response Criteria

Evaluation of Target Lesions

Complete Response (CR): Disappearance of all target lesions. Any pathological lymph nodes (whether target or non-target) must have reduction in short axis to <10 mm.

Partial Response (PR): At least a 30% decrease in the sum of the diameters of target lesions, taking as reference the baseline sum diameters and not qualifying for progressive disease criteria.

Progressive Disease (PD): At least a 20% increase in the sum of the diameters of target lesions, taking as reference the smallest sum on study (this includes the baseline sum if that is the smallest on study). In addition to the relative increase of 20%, the sum must also demonstrate an absolute increase of at least 5 mm. (Note: the appearance of one or more new lesions is also considered progressions).

Stable Disease (SD): Neither sufficient shrinkage to qualify for PR nor sufficient increase to qualify for PD, taking as reference the smallest sum diameters while on study.

Evaluation of Non-Target Lesions

Complete Response (CR): Disappearance of all non-target lesions and normalization of tumor marker level. All lymph nodes must be non-pathological in size (<10 mm short axis).

Note: If tumor markers are initially above the upper normal limit, they must normalize for a patient to be considered in complete clinical response.

Non-CR/Non-PD: Persistence of one or more non-target lesion(s) and/or maintenance of tumor marker level above the normal limits.

Progressive Disease (PD): Appearance of one or more new lesions and/or *unequivocal progression* of existing non-target lesions. *Unequivocal progression* should not normally trump target lesion status. It must be representative of overall disease status change, not a single lesion increase.

Although a clear progression of “non-target” lesions only is exceptional, the opinion of the treating physician should prevail in such circumstances, and the progression status should be confirmed at a later time by the review panel (or Principal Investigator).

Evaluation of Best Overall Response

The best overall response is the best response recorded from the start of the treatment until disease progression/recurrence/death (whichever happens first) (taking as reference for progressive disease the smallest measurements recorded since the treatment started). The patient's best response assignment will depend on the achievement of both measurement and confirmation criteria.

For Patients with Measurable Disease (*i.e.*, Target Disease)

Target Lesions	Non-Target Lesions	New Lesions	Overall Response	Best Overall Response when Confirmation is Required*
CR	CR	No	CR	≥4 wks. Confirmation*
CR	Non-CR/Non-PD	No	PR	≥4 wks. Confirmation*
CR	NE	No	PR	
PR	Non-PD/NE	No	PR	
SD	Non-PD/NE	No	SD	Documented at least once ≥4 wks. from treatment start*
Not all evaluated	Non-PD	No	NE	=
PD	Any	Yes or No	PD	--
Any	PD**	Yes or No	PD	
Any	Any	Yes	PD	

* See RECIST 1.1 manuscript (Eisenhauer et al Eur J Cancer 2009) for further details on what is evidence of a new lesion.
 
Only for non-randomized trials with response as primary endpoint.
 
** In exceptional circumstances, unequivocal progression in non-target lesions may be accepted as disease progression.
 
NE = non evaluable
 
Note: Patients with a global deterioration of health status requiring discontinuation of treatment without objective evidence of disease progression at that time should be reported as “symptomatic deterioration.” Every effort should be made to document the objective progression even after discontinuation of treatment.
				

For Patients with Non-Measurable Disease (i.e., Non-Target Disease)

Non-Target Lesions	New Lesions	Overall Response
CR	No	CR
Non-CR/non-PD	No	Non-CR/non-PD*
Not all evaluated	No	NE
Unequivocal PD	Yes or No	PD
Any	Yes	PD

* ‘Non-CR/non-PD’ is preferred over ‘stable disease’ for non-target disease since SD is increasingly used as an endpoint for assessment of efficacy in some trials so to assign this category when no lesions can be measured is not advised
 
NE = non evaluable
		

Confirmatory Measurement/Duration of Response

Confirmation

To be assigned a status of PR or CR, changes in tumor measurements must be confirmed by repeat assessments that should be performed ≥ 4 weeks after the criteria for response are first met. In the case of SD, follow-up measurements must have met the SD criteria at least once after study entry at an interval of ≥ 4 weeks).

Duration of overall response: The duration of overall response is measured from the time measurement criteria are met for CR or PR (whichever is first recorded) until the first date that recurrent or progressive disease is objectively documented (taking as reference for progressive disease the smallest measurements recorded since the treatment started).

The duration of overall CR is measured from the time measurement criteria are first met for CR until the first date that progressive disease or death due to study indication (whichever happens first) objectively documented.

Duration of stable disease: Stable disease is measured from the start of the treatment until the criteria for progression or death due to study indication (whichever happens first) are met, taking as reference the smallest measurements recorded since the treatment started, including the baseline measurements.

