1.2.1.2.2 Preliminary efficacy of BGJ398 (infigratinib)

CBGJ398X2101

Preliminary antitumor efficacy has been shown in patients treated at ≥ 100 mg in squamous NSCLC and urothelial carcinoma with FGFR genetic alterations. As of 15 May 2015, 4/36 patients with NSCLC and 3/8 patients with urothelial carcinoma achieved PR (Nogova L et al JCO 2017). In addition, as of 1 Mar 2016, of 37 evaluable patients in a dedicated arm for urothelial carcinoma, 12 achieved PR, and 1 achieved CR (Pal et al ASCO 2016).

CBGJ398X2102

Preliminary anti-tumor activity has been detected in patients treated at doses of ≥ 100 mg of BGJ398 in combination with 300 mg BYL719. This activity has been detected in patients with the following tumor types; bladder, breast, ovarian, and head and neck.

CBGJ398X2204

Preliminary antitumor activity has been observed in cholangiocarcinoma patients harboring FGFR2 fusion or other FGFR genetic alteration treated with 125mg BGJ398 on 3 weeks on, 1 week off schedule. Of the 63 patients enrolled to the BGJ398X2204 study, there were 59 patients evaluable for efficacy (with valid baseline and at least one valid post-baseline assessment). Out of these 59 patients, 15 (23.8%) patients had BOR of confirmed partial response and 33 (52.4%) experienced BOR of stable disease. Therefore, the primary endpoint of investigator-assessed ORR (confirmed responses only) is 23.8%. Disease control rate is 76.2% (48 patients). Additionally, out of the 33 patients who achieved stable disease, 4 patients achieved PR in one scan (did not have subsequent scan confirming the PR). The median PFS is estimated at 6.7 months (95% CI: 4.8-7.6 months). Of the 63 patients, 49 (77.8%) had a PFS event (4 deaths and 45 patients progressed as per RECIST). (Javle M et al JCO 2018)

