Head and neck cancer (HNC) is the 6th most common cancer worldwide (~50,000 cases/year in the US; 60,000 cases/year in Europe). Once recurrent or metastatic, head and neck cancer carries a poor prognosis with a median survival of only 6-10 months ([Vermorken et al. 2008](#); [Seiwert et al. 2008](#)). Cetuximab is the only approved targeted therapy for this disease and the response rate is 13% ([Vermorken et al. 2007](#); [Seiwert et al. 2012](#)). Better treatments are needed.

Over the past decade, it has become clear that HPV-related (HPV (+)) head and neck cancer represents a distinct epidemiologic, molecular, pathologic, and clinical entity. In recent years, HNSCC, in particular, oropharyngeal cancer, has shown a sharp increase in incidence related to oncogenic HPV16 infections ([Marur et al. 2010](#)). These cancers arise almost exclusively in the oropharynx (base of tongue and tonsil) for reasons that have not yet been identified, and tend to affect younger patients, appear to metastasize early to regional lymph nodes, and carry better prognosis than “classic” smoking and alcohol related, HPV (-) HNSCC ([Marur et al. 2010](#)). Interestingly, up to 70% of oropharyngeal cancers in several developed countries, including the US, is felt to be HPV-related ([Chaturvedi et al. 2011](#)). HPV has also been detected in smaller subsets of laryngeal and oral cavity cancers, though these estimates are closer to 10% ([Halec et al. 2013](#)). HPV origin of HNSCC in individual patients can be established by direct assessment of HPV based on detection of HPV DNA or RNA (i.e. in situ hybridization or PCR). However, more frequently, p16 immunohistochemistry can serve as a surrogate marker for oropharyngeal cancers, albeit concerns about accuracy have been voiced ([Vokes et al. 2013](#)).

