3.2 Secondary Objectives

	Objective	Endpoint/Analysis
Secondary	Assess safety and tolerability of BGJ398 (infigratinib) in patients with Head and Neck Cancer	AE / SAE
Secondary	Assess duration of response, progression free and overall survival	DOR / PFS* / OS**

*Progression-free survival [days] = date of progression (or of death if no earlier progression) – date of randomization +1

*Progression-free survival (censored) [days] = date of last adequate assessment per RECIST 1.1 with negative imaging before patient withdrawal of consent or start of new therapy – date of randomization +1

**Overall survival [days] = date of death – date of randomization +1

Trial termination is synonymous with off study / end of treatment.

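### No death ends the duration of overall response, and only cancer deaths end the CR and stable-disease durations, whereas PFS counts every death without earlier progression

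*Combined protocol and SAP*

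**What the plan says.** Section 7.3.1, under Confirmatory Measurement/Duration of Response, defines three durations with two end rules.

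- Overall response (CR or PR) runs "until the first date that recurrent or progressive disease is objectively documented". Death is not mentioned.
- CR runs "until the first date that progressive disease or death due to study indication (whichever happens first) objectively documented".
- Stable disease runs "until the criteria for progression or death due to study indication (whichever happens first) are met".

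Section 3.2 lists duration of response as a secondary endpoint beside PFS and overall survival. It dates the PFS event as "date of progression (or of death if no earlier progression", with no restriction on cause of death. Its only censoring rule is for PFS: "date of last adequate assessment per RECIST 1.1 with negative imaging before patient withdrawal of consent or start of new therapy".

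Section 11.1 gives Kaplan-Meier methods for PFS and overall survival. For duration of response and of stable disease it says only that they will be reported. Section 10.6 provides for collecting progression and death after a patient has left the study.

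**The concern.** Duration of response describes how long a benefit lasts, and a responder who dies no longer has that benefit. As written, the death is an event for PFS, is an end of CR or stable disease only if attributed to the cancer, and is never an end of overall response. The same patient can thus have durations that disagree with each other and with PFS.

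The situation is foreseeable. Scans are 8 weeks apart, and by the footnote to the assessment schedule they run until progression or end of treatment. A responder who stops for toxicity therefore has no further scheduled imaging. Section 2 states that once recurrent or metastatic, "head and neck cancer carries a poor prognosis with a median survival of only 6-10 months".

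At stake is the secondary duration-of-response result, together with the CR and stable-disease durations. With few responders, a handling rule chosen after the data are seen could change the reported median.

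**Working it through.** **1. The rules side by side.** The table shows whether each event ends each measure as the text stands.

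| Event | PFS (3.2) | Overall response (7.3.1) | CR (7.3.1) | Stable disease (7.3.1) |
|---|---|---|---|---|
| Documented progression | yes | yes | yes | yes |
| Cancer death, no documented progression | yes | no | yes | yes |
| Other death, no documented progression | yes | no | no | no |

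**2. Is the gap closed elsewhere?** No. The censoring rule in 3.2 is for PFS and covers withdrawal of consent or new therapy. Section 11.1 gives no event or censoring rule for durations. Within 7.3.1 itself, the window for best overall response closes at progression, recurrence or death, with no restriction on cause, so the section is not consistent with itself.

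**3. Number of responders.** The plan states no figure for duration to reproduce. Its 20 patients and 21% target rate (Sections 4.7 and 11.1) give 20 x 0.21 = 4.2, so about 4 responders.

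**4. How often might it happen?** The only related figure is from the earlier cholangiocarcinoma study (Section 1.2.1.2.2): of 63 patients, "49 (77.8%) had a PFS event (4 deaths and 45 patients progressed as per RECIST". That is 4/49 = 8.2% of PFS events. It covers all patients in another cancer, not responders here. Taken as a rough guide, it gives 4.2 x 0.082 = 0.34 expected deaths among responders. The chance of at least one among four is 1 - (1 - 0.082)^4 = 0.29.

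**5. Size if such deaths are censored, large sample.** Let f be the share of first events that are uncounted deaths. With independent constant hazards, censoring them multiplies the any-cause median by 1/(1 - f). From an assumed any-cause median of 6.0 months:

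| f (assumed) | Factor | Median, months |
|---|---|---|
| 5% | 1.053 | 6.3 |
| 8% | 1.09 | 6.5 |
| 10% | 1.111 | 6.7 |
| 20% | 1.250 | 7.5 |
| 30% | 1.429 | 8.6 |

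**6. Size with four responders.** Take invented durations of 3, 5, 7 and 9 months.

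- All four counted: S(3) = 0.75, S(5) = 0.50, median 5.
- The 3 is a censored death: S(5) = 2/3 = 0.667, S(7) = 0.333, median 7.
- The 5 is a censored death: S(3) = 0.75, S(7) = 0.75 x 1/2 = 0.375, median 7.
- The 7 or the 9 is a censored death: S(5) = 0.50, median stays 5.

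So the median moves only if the uncounted death is one of the two earliest.

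A simulation used four responders, a 6-month any-cause median, 8-week scans and deaths censored at the last scan. Censoring lengthened the Kaplan-Meier median in 15% of runs at f = 8%, 37% at f = 20% and 50% at f = 30%. It shortened the median in none.

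**The case against.** The best defence is that no bias has been shown. The documents do not say these deaths are censored, so a reader who infers that reported durations will be too long goes further than the text. If such patients were simply left out, the direction would depend on who they are. This stands: the upward bias is conditional on censoring. The mismatch between the end rules is not conditional on anything.

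Two other inferences go too far. One is that every patient who dies without a progression scan lacks an end date. For CR and stable disease a cancer death does supply one; only overall response ignores all deaths. The other is that the investigator decides the cause of death. The documents assign adverse-event causality to the site investigator, but they do not say who attributes a death for these durations.

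The size may also be small. At f = 8% the modelled shift is about half a month, well under one 8-week scan interval, and most simulated medians did not change. The 6-10 month median survival does not show how often responders die before documented progression. The plan asks for every effort to document progression after discontinuation, accepts clinically prompted mid-cycle scans, and reports PFS and overall survival alongside. These points limit the frequency and the harm. They do not supply an end rule for a death that still occurs without documented progression.

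**Conclusion.** The point holds as an inconsistency in stated definitions. Followed as written, Section 7.3.1 never ends overall response at a death, and ends CR and stable disease only at cancer deaths. PFS counts every death without earlier progression, and no other section reconciles them.

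If the uncounted deaths are censored, the bias is upward: 5% to 43% in the median for f from 5% to 30%, assuming constant independent hazards. With about four responders, one early uncounted death can move the median noticeably, and a late one need not move it at all. The true f in this trial is unknown, and 4/49 is only a rough guide.

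A reader might infer that the trial's main conclusion is affected. It is not: the objective response rate, the two-stage rule, sample size, PFS and overall survival do not use these definitions. The effect is confined to duration of response as a secondary endpoint and to the CR and stable-disease durations.

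**What to change.** In Section 7.3.1:

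- End all three durations at the first of documented progression (or recurrence) or death from any cause.
- Start overall response duration at the first documented CR or PR, CR duration at the first documented CR, and stable-disease duration at the start of treatment.
- Censor patients without an event, including those still responding at the analysis, at the last adequate RECIST assessment (before withdrawal of consent or new therapy, where these apply).

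Pointing to the PFS rule in Section 3.2 would not be enough. It covers only withdrawal of consent or new therapy, so it gives no date for a patient still in response. Its formula also runs from a randomization date, which a single-arm trial does not have.

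The cost is wording only, since Section 10.6 already collects progression and death after removal from study. Reported durations may be slightly shorter.
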